### **8. Research Question and Objectives**

The aim of this study is to describe the real-world use of ESAs in cancer patients with non-myeloid malignancies receiving myelosuppressive chemotherapy in Europe and the UK, specifically to establish whether ESAs are being used according to the product label and consistent with Study 20070782.

#### **8.1 Primary**

- Describe the baseline Hb levels at initiation of treatment with ESA in patients receiving myelosuppressive chemotherapy

#### **8.2 Secondary**

- Describe the baseline demographic and clinical characteristics of patients initiating treatment with an ESA and receiving myelosuppressive chemotherapy
- Describe the duration of ESA prescription in subjects receiving myelosuppressive chemotherapy
- Describe the dose distribution of treatment with ESA in patients receiving myelosuppressive chemotherapy at (a) first prescription of an ESA and (b) subsequent ESA prescriptions (where available). Dose will be categorized by long-acting and short-acting ESAs to avoid dose conversion.

- Describe Hb levels during treatment with ESAs in patients receiving myelosuppressive chemotherapy.
- Describe the number of patients with a “rapid” rise in Hb level (considered to be more than 2 g/dL in any 4-week period), and whether patients with a rapid rise in Hb have a subsequent ESA dose reduction or therapy interruption.

## 9. Research Methods

### 9.1 Study Design

This study will be a retrospective multi-centre observational study conducted in 6 countries: France, Germany, Italy, Spain, the United Kingdom, and Belgium . It will document real-world ESA-related measures in patients with non-myeloid malignancies treated with chemotherapy at university hospitals, community hospitals, private practice and community-based clinics typical of those that treat patients for whom ESAs are indicated.

### 9.2 Setting and Study Population

#### 9.2.1 Study Period

The study period is anticipated to include data spanning from January 2015 (based on updated guidance by the National Institute for Health and Care Excellence [NICE] at the end of 2014; NICE 2014) until last patient enrolled. Erythropoiesis Stimulating Agents treatment initiation (the prescription date) will be considered the study index date. Patients will be followed from the index date until 9 weeks post-index date or if 1 of the following criteria is met: ESA treatment end date, death, or date of consent/enrolment, whichever comes first. Baseline data to provide details on the patient’s medical condition prior to use of ESA may include data from medical records prior to January 2015.

#### 9.2.2 Selection and Number of Sites

This study aims to enroll patients from **approximately 24** sites drawn from **countries within the EU** and the United Kingdom. If the number of potential patients from the final list of selected sites falls below the planned sample size, additional sites within the **countries** already identified may be included. Sites will be approached based on physicians who prescribe ESAs and target where possible Oncologists and Haematologists who are prescribing ESAs.

### 9.2.3 Subject/Patient/Healthcare Professional Eligibility

#### 9.2.3.1 Inclusion Criteria

Patients will be included in the study if they meet all the following criteria:

- At least 1 recorded primary diagnosis for any non-myeloid malignancy within 1 year before index date (ie, ESA treatment initiation) preceding the first chemotherapy administration
- At least 1 administration for a myelosuppressive chemotherapy drug (any line of therapy) before index date
- At least 1 administration of an ESA during the study period
- A minimum of a 9-week period between ESA treatment initiation and enrolment/consent
- Aged  $\geq$  18 years at index date
- Medical records (including diagnosis, demographics) are available for review and data extraction
- At least 1 Hb recording on or before the index date (the most proximal laboratory value available within 4 weeks prior to index date will be collected).
- Have provided written informed consent or appropriate parties have been notified of participation (alive or deceased), where required for access to medical charts, according to local laws and regulation requirements.

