Describe the baseline Hb levels at initiation of treatment with ESA in patients receiving myelosuppressive chemotherapy	Hb level in g/dL at initiation of ESA, further categorised in 2 alternative ways, as per product label and clinical trial criteria 
 
• Hb <math>\leq</math> 10 g/dL
 
• Hb <math>\leq</math> 11 g/dL
 

Secondary	
Describe the baseline demographic and clinical characteristics of patients initiating treatment with an ESA and receiving myelosuppressive chemotherapy	Demographic characteristics (age and sex), comorbidities, type of malignancy, type of chemotherapy treatment received, red blood cell (RBC) transfusions
Describe the duration of ESA prescription in subjects receiving myelosuppressive chemotherapy	Average prescription length of ESA, number of patients prescribed ESA at weeks 3, 4, 6, and 9
Describe the dose distribution of treatment with ESA in patients receiving myelosuppressive chemotherapy at (a) first prescription of an ESA and (b) subsequent ESA prescriptions (where available)	Prescribed dose, dose frequency, dose modifications.
Describe Hb levels during treatment with ESA in patients receiving myelosuppressive chemotherapy	Hb level during ESA treatment: 
 
• Below target level (<math>\leq</math> 10 g/dL)
 
• Target range (<math>></math> 10 to <math>\leq</math> 12 g/dL)
 
• Above target level (<math>></math> 12 g/dL)
 

Describe the number of patients with a “rapid” rise in Hb level (considered to be more than 2 g/dL in any 4-week period), and whether patients with a rapid rise in Hb have a subsequent ESA dose reduction or therapy interruption	Change in Hb level during ESA treatment, categorised: 
 
• More than 2 g/dL rise in any 4-week period
 
• More than 2 g/dL rise in any 4-week period that did not have a subsequent ESA dose reduction or therapy interruption
 

- *Hypothesis/Estimation*

This is an estimation study and no hypotheses will be tested.

- *Study Design/Type:*

Retrospective medical chart review.

- *Study Population or Data Resource*

The study will include patients diagnosed with any non-myeloid malignancy who initiate treatment with an ESA while receiving chemotherapy and were not previously treated with an ESA.

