## 7. Rationale and Background

### 7.1 Diseases and Therapeutic Area

Anaemia is a reduction of haemoglobin (Hb) concentration below normal levels of 12 g/dL. It is a common complication in patients with cancer (Aapro et al, 2018). Between 30% and 60% of patients with non-haematological and haematological malignancies, will develop anaemia, and the incidence of anaemia is even higher in patients treated with myelosuppressive chemotherapy (> 60%) (Ludwig et al, 2004).

Treatment options for the management of CIA include adjustments to the cancer treatment regimen, RBC transfusions, ESAs, and iron supplementation either alone or in combination with ESAs (Aapro et al, 2018). Most chemotherapy patients who develop anaemia do not receive any treatment, but patients with a moderate or severe anaemia may be given RBC transfusions. The major aims of anaemia treatment are the reduction of symptoms, particularly fatigue, and an improved quality of life.

Amgen's darbepoetin alfa (Aranesp®) is indicated in the EU for treatment of symptomatic anaemia in adult cancer patients with non-myeloid malignancies receiving chemotherapy. Aranesp® should be administered only to patients with a Hb concentration ≤ 10 g/dL and used to achieve a target Hb of not greater than 12 g/dL.

In 2008, a class safety review was initiated because clinical trial data showed a consistent unexplained excess mortality and/or tumour progression in cancer patients

with anaemia treated with ESAs. As a consequence, the SmPC was updated and it was considered that routine pharmacovigilance measures (eg, its use according to the label) would be adequate to mitigate this risk (Aranesp SmPC).

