#### **9.7.2.4 Analysis of the Primary, Secondary, and Exploratory Endpoint(s)**

##### Primary endpoint

The number and proportion (%) of patients receiving myelosuppressive chemotherapy with a baseline Hb level of  $\leq 10$  g/dL (as per SmPC), and  $\leq 11$  g/dL (as per Study 20070782) prior to or at initiation of ESA treatment will be summarised with descriptive statistics overall and stratified by ESA type, type of malignancy, and country.

The variable will be expressed both as continuous (mean, SD, median, min and max) and categorical ( $\leq 10$  g/dL vs  $> 10$  g/dL and  $\leq 11$  g/dL vs  $> 11$  g/dL), in accordance with **the** SmPC and Study 20070782 categorization.

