#### Selection of patients

To avoid selection bias when selecting patients, the following measures will be in place:

- The inclusion criteria will be kept minimal to maximise generalisability.
- Patient characteristics will be compared with other published studies on ESA utilisation.

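### Inclusion requires one past chemotherapy dose, not chemotherapy ongoing at ESA start, so starts after chemotherapy ended enter the primary Hb proportions without being separated

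*Protocol*

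**What the plan says.** Section 9.2.3.1, like the eligibility summary in the Abstract, sets the chemotherapy requirement as "At least 1 administration for a myelosuppressive chemotherapy drug (any line of therapy) before index date". No exclusion in section 9.2.3.2 removes a patient who had finished chemotherapy. The only other timing rule is the diagnosis bullet, which asks for a diagnosis "within 1 year before index date (ie, ESA treatment initiation) preceding the first chemotherapy administration".

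Elsewhere the population is described more narrowly:

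- The Abstract (Study Population) speaks of patients "who initiate treatment with an ESA while receiving chemotherapy and were not previously treated with an ESA".
- Section 9.5 sizes the study for patients given an ESA during chemotherapy, and the primary objective in section 8.1 has the same population.
- The primary endpoint in section 9.7.2.4 is "The number and proportion (%) of patients receiving myelosuppressive chemotherapy with a baseline Hb level of" 10 g/dL or less (as per the SmPC) and 11 g/dL or less (as per Study 20070782).
- Section 7.1 gives the EU indication as "treatment of symptomatic anaemia in adult cancer patients with non-myeloid malignancies receiving chemotherapy".

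The aim in section 8 is "specifically to establish whether ESAs are being used according to the product label and consistent with Study 20070782". Chemotherapy timing is a covariate in section 9.3.3, and section 9.7.2.4 undertakes to describe each covariate listed there.

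**The concern.** The list that sites enrol against does not deliver the population that the objective and endpoint name. The indication as cited has at least two parts that can be checked from a chart: the Hb level and being on chemotherapy. The primary outcome examines only the first and takes the second as given, although eligibility does not secure it.

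This matters because the study asks whether use follows the label and resembles Study 20070782, whose patients were receiving multi-cycle chemotherapy. Section 7.2 says that a substantial prevalence of use inconsistent with that trial may warrant a mortality study. ESA use after chemotherapy has ended is one such pattern, and the protocol's main results do not set it apart.

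**Working it through.** **Can a post-chemotherapy start qualify?** Take an illustrative patient diagnosed 11 months before index, with first chemotherapy 10 months before, last dose 6 months before, and index Hb 9.5 g/dL. The diagnosis falls within the year and precedes the first dose, at least one dose precedes index, and no exclusion applies. The patient is eligible, is in the denominator, and counts in the proportion at or below 10 g/dL. On a strict reading of the diagnosis bullet the order is diagnosis, first dose, index, all within one year. The gap since chemotherapy is then bounded at about 12 months, but a gap of several months is still allowed.

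**Is it separated anywhere?** The subgroups in section 9.7.2.5.1 are ESA type, tumour type and country. The sensitivity analysis in section 9.7.2.5 concerns red cell transfusion within 28 days. Chemotherapy timing is described as a covariate but does not define any analysis set.

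**The plan's own precision.** The Clopper-Pearson half-width, (upper − lower)/2 with x = np, reproduces Table 1: 0.024793 at n = 1600, p = 0.5, and 0.024831 at n = 600, p = 0.9. At the planned n = 1625 it is 0.0246 at p = 0.5, 0.0219 at p = 0.73 and 0.0149 at p = 0.9.

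**Two quantities to keep apart.** Let f be the share of starts after chemotherapy ended, and q_off and q_on the shares with Hb of 10 g/dL or less in those starts and in the rest. The documents give none of these. I assume f from 2% to 20%. The value 0.73 is borrowed from the Central and Eastern European study cited in section 9.5 (which used below 10 g/dL), and 0.5 and 0.9 are the ends of Table 1.

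*(a) Share of the cohort meeting the Hb cut-off while outside the cited indication: f × q_off.*

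| f | patients of 1625 | q_off = 0.5 | q_off = 0.73 | q_off = 0.9 |
|---|---|---|---|---|
| 2% | about 32 | 1.0% | 1.46% | 1.8% |
| 5% | about 81 | 2.5% | 3.65% | 4.5% |
| 10% | about 162 | 5.0% | 7.3% | 9.0% |
| 20% | 325 | 10.0% | 14.6% | 18.0% |

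*(b) Shift in the Hb proportion compared with patients on chemotherapy only: f × (q_off − q_on).* With q_on = 0.73:

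| f | q_off = 0.5 | q_off = 0.73 | q_off = 0.9 |
|---|---|---|---|
| 5% | −1.15 points | 0 | +0.85 points |
| 10% | −2.3 points | 0 | +1.7 points |
| 20% | −4.6 points | 0 | +3.4 points |

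The half-width of 2.19 points at p = 0.73 is the right yardstick for (b) only. The shift passes it when f exceeds 0.0219/0.23 = 9.5% (q_off = 0.5) or 0.0219/0.17 = 12.9% (q_off = 0.9). Quantity (a) is a different estimand, which the protocol does not plan to report.

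**The case against.** The strongest reply has four parts.

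**The population is stated and timing will be reported.** The Abstract says the ESA is started during chemotherapy, and section 9.7.2.4 describes every covariate in section 9.3.3, including chemotherapy timing. A reader might infer that post-chemotherapy starts are hidden. They are not: the data are collected and described, and the detailed tabulation may sit in an analysis plan that is not at hand. What stands is that the Abstract's phrase is not a criterion, and that a marginal description of timing does not show how many of these starts fall within the primary proportions.

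**No endpoint labels a patient as label-consistent.** This is correct. The SmPC reference is attached to the Hb cut-off. But with the aim in section 8 as worded, the Hb proportion will naturally be read as the measure of label adherence.

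**The primary proportion need not be biased.** Also correct. A reader might take quantity (a) as the error in the Hb result. The error is (b), which is zero if Hb at start is distributed alike on and off chemotherapy.

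**The diagnosis rule limits the interval.** It does on a strict reading, so it would be wrong to say that there is no time limit at all. A bound of about 12 months does not make chemotherapy ongoing.

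A reader might also infer from the diagnosis bullet that later-line or relapsed patients are excluded. That follows only if the bullet means a first diagnosis within the year. It could equally mean any diagnosis record in that year, which fits better with any line of therapy being allowed and with "The inclusion criteria will be kept minimal to maximise generalisability" in section 9.9.1.3. The wording is ambiguous, and the exclusion is not established.

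**Conclusion.** The point holds as a mismatch between the operative criterion and the stated population. As written, section 9.2.3.1 lets patients whose chemotherapy had ended, by up to about 12 months on a strict reading, into the primary denominator and into the proportion at or below 10 g/dL. No primary, subgroup or sensitivity analysis in the protocol sets them apart.

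The size cannot be derived from the documents. Under the assumed f of 2% to 20% and Hb shares of 0.5 to 0.9, between 1% and 18% of the cohort would meet the Hb cut-off while outside the chemotherapy part of the cited indication. The width of that range reflects ignorance of f. The effect on the Hb proportion is smaller and may be nil. The case for acting rests on the study's question about label use, not on a demonstrated bias in the primary estimate. The documents do not support a claim that the pattern is concealed or that later-line patients are lost.

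**What to change.** 1. From the chemotherapy dates already collected, derive a flag for chemotherapy ongoing at index, based on the interval from the last dose on or before index. The sponsor chooses the window and fixes it before the interim analysis. The flag should not depend on a later cycle being given, because that would define a baseline set by events after index.
2. Report the primary Hb proportions in flagged patients and in all enrolled patients. Report the number and proportion of remaining starts as not matching the chemotherapy part of the indication in section 7.1.
3. Reconcile sections 5, 8.1, 9.2.3.1, 9.5 and 9.7.2.4 so that the population carries one definition.
4. State whether the 1-year diagnosis bullet means a diagnosis record within the year or a first diagnosis within the year, and reconcile it with the any-line wording.

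The first two items need no new data and remove nobody from the study; the cost is a derived variable and one extra table row. The flagged set is somewhat smaller. At f = 10% it has about 1625 × 0.9 = 1462 patients, between the Table 1 rows for 1400 and 1500, so the half-width at p = 0.5 lies between 2.56 and 2.65 points, against 2.46 for all 1625. At f = 20% it has 1300 patients and a half-width of 2.75 points. Changes to protocol wording carry the amendment steps of section 12.1. If sites have applied the diagnosis bullet in different ways, the report should say so.

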#### 9.2.3.2 Exclusion Criteria

Patients will be excluded from the study if they meet any of the following criteria:

- A diagnosis of chronic or acute kidney disease-induced anaemia 1 year before index date
- A diagnosis of myelodysplastic syndrome within 1 year before index date
- ESA administration prior to the index date
- Index ESA administration before 1 January 2015

#### 9.2.4 Matching

Not applicable.

#### 9.2.5 Baseline Period

The baseline period is considered 1 year before index date. Collection of comorbidities and associated ongoing concomitant medications may include data prior to this period.

#### 9.2.6 Study Follow-up

All information relating to an individual patient will be collected retrospectively using medical records. All ESA treatment episodes will be collected from the index date until 9 weeks post-index date or if 1 of the following criteria is met: ESA treatment end date, death, or date of consent/enrolment, whichever comes first.

### 9.3 Variables

#### 9.3.1 Exposure Assessment

The main exposure for the study will be treatment with ESAs – either darbepoetin alfa or epoetin (any type). Information on use of an ESA treatment will be determined by the presence of 1 or more prescriptions for an ESA as recorded in the EMR, including time of each administration (if available), dose and type of ESA.

- Date of ESA prescriptions
- Type of ESA
- Frequency of ESA administration (where available)
- Dose of ESA
  - Recorded dose at each prescription
  - Dose modifications: recorded as raw values and categorised and reported as nominal categorical variables: dose increase/dose decrease/interruption.
- Total duration of ESA prescription will be calculated and expressed in number of weeks on treatment, and by number with prescription duration of 3, 4, 6, and 9 weeks.

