##### Secondary outcome

For Hb levels during treatment, all available measurements during ESA treatment will be collected per patient.

Hb values achieved at pre-specified time points during treatment (ie, 3 weeks, 4 weeks, 6 weeks, and 9 weeks) will be reported. These time points are in line with recommended dosing intervals of the SmPC and Study 20070782.

The baseline demographic and clinical characteristics of patients initiating treatment with an ESA and receiving myelosuppressive chemotherapy will be described as the number and proportion (%) for each of the covariates listed in Section 9.3.3.

The duration of prescription will be collected for each ESA prescription. The mean duration of prescription will be described, and the number and proportion (%) of patients with an ESA prescription at 3, 4, 6, and 9 weeks will be described.

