##### Secondary endpoints

The baseline demographic and clinical characteristics of patients initiating treatment with an ESA and receiving myelosuppressive chemotherapy will be described as the number and proportion (%) for categorical variables, or as means, SD, median, min and max for continuous variables, for each of the covariates listed in Section 9.3.3, and stratified by ESA type, type of malignancy, and country.

The frequency of ESA treatment, the number of ESA prescriptions, and the duration of ESA prescriptions will be summarized with descriptive statistics overall and stratified by ESA type, type of malignancy, and country. The number and proportion (%) of patients prescribed an ESA for 3, 4, 6, and 9 weeks will be reported.

The starting dose will be summarized with descriptive statistics by ESA type. The number and proportion (%) of patients with at least 1 dose modification will be reported

overall, and (where available) by type of dose modification (eg, dose reduction, dose escalation, therapy interruption).

The number and proportion (%) of patients with 1 or more repeated Hb measures after baseline will be reported.

Hb values reached at pre-specified time points during treatment (ie, 3 weeks, 4 weeks, 6 weeks, and 9 weeks) will be described.

Hb values during treatment will be described in terms of:

- Mean, standard deviation, median, interquartile range, minimum, maximum values.
- The proportion of patients reaching the target Hb level, expressed as:
  - Below target level ( $\leq 10$  g/dL)
  - Target range ( $> 10$  to  $\leq 12$  g/dL)
  - Above target level ( $> 12$  g/dL)
- The proportion of patients at week 9 who:
  - Had a rise in Hb of more than 2 g/dL in any 4-week period
  - Had a rise in Hb of more than 2 g/dL in any 4-week period that did not have a subsequent ESA dose reduction or therapy interruption

Handling of multiple measurements per patients:

All Hb values as recorded within  $\pm 6$  days around each time point of interest (3, 4, 6, and 9 weeks) will be used to inform on the values to be reported for this study. The mean and median value for each patient will be calculated for each time point. For example, at 3 weeks (day 21), the mean and median of all Hb values recorded in days 15-27 will be calculated.

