#### 9.7.2.5.1 Subgroup Analysis

The primary and secondary objectives will be reported according to the following subgroups:

- Type of ESA (darbepoetin alfa or epoetin)
- Type of primary tumour (all lung [and NSCLC separately], breast cancer total, adjuvant-treated breast cancer, metastatic breast cancer, colorectal cancer, or lymphoma). Patients diagnosed with other non-myeloid tumour types will not be evaluated as specific subgroups
- Country: Belgium, France, Germany, Italy, Spain, **and** the United Kingdom

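### Starting dose and dose modification are defined on the dose per prescription without the dosing interval, so schedules are pooled and schedule changes may be misclassified or missed

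*Protocol*

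**What the plan says.** Protocol Section 9.3.1 lists the items that make up exposure. Under dose it has "Recorded dose at each prescription", followed by "Dose modifications: recorded as raw values and categorised and reported as nominal categorical variables: dose increase/dose decrease/interruption". The dosing interval is a different bullet, "Frequency of ESA administration (where available"), and is not mentioned in the modification rule.

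Section 9.7.2.4 keeps the two apart in the analysis. For dose: "The starting dose will be summarized with descriptive statistics by ESA type". For frequency, in another paragraph: "The frequency of ESA treatment, the number of ESA prescriptions, and the duration of ESA prescriptions will be summarized with descriptive statistics overall", with strata by ESA type, malignancy and country. Section 9.7.2.5.1 gives ESA type two levels, darbepoetin alfa and epoetin. Section 8.2 words the dose grouping differently: "Dose will be categorized by long-acting and short-acting ESAs to avoid dose conversion".

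Section 9.3.2 explains the choice of the 3-, 4-, 6- and 9-week Hb time points: "These time points are in line with recommended dosing intervals of the SmPC and Study 20070782". The plural shows that more than one dosing interval is expected.

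Sections 8.2 and 9.7.2.4 also have an endpoint that depends on detecting a reduction: a rise in Hb of more than 2 g/dL in any 4-week period with no later ESA reduction or interruption. The abstract (Section 5) describes the complementary count, and there takes the reduction or interruption from the medical notes.

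**The concern.** Exposure to an ESA is dose divided by interval. A dose per prescription has no time unit, so two patients with the same weekly exposure can have different recorded doses, and a patient whose weekly exposure is cut can have the same recorded dose throughout. The three categories in Section 9.3.1 (increase, decrease, interruption) have no place for a change of schedule.

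Two results are exposed. The first is the secondary objective on the dose distribution at first and later prescriptions. The second is the rapid-rise endpoint. The abstract ties it to SmPC guidance on responding to a rapid rise, so it bears directly on the study's aim of checking consistency with the label. A missed reduction there is counted as a failure to act.

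**Working it through.** The protocol states no figure on this point, so there is none to reproduce. The check compares the dose as recorded with dose per week. D is an arbitrary dose unit. The doses and intervals below are chosen for illustration and are not taken from the protocol.

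**Step 1: dose changes.** For a move from dose d0 every i0 weeks to d1 every i1 weeks:

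- raw ratio = d1 / d0
- weekly ratio = (d1 / i1) / (d0 / i0)

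| From | To | Raw ratio | Reads as | Weekly ratio | Weekly exposure |
|---|---|---|---|---|---|
| D every week | 3D every 3 weeks | 3.0 | increase | 1.0 | unchanged |
| D every week | 2D every 3 weeks | 2.0 | increase | 0.67 | lower |
| 3D every 3 weeks | D every week | 0.33 | decrease | 1.0 | unchanged |
| 3D every 3 weeks | 1.5D every week | 0.5 | decrease | 1.5 | higher |
| D every week | D every 2 weeks | 1.0 | no change | 0.5 | lower |
| D every week | D every 3 weeks | 1.0 | no change | 0.33 | lower |
| 3D every 3 weeks | 3D every 4 weeks | 1.0 | no change | 0.75 | lower |

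The raw dose can therefore mislead in either direction, and can show nothing when weekly exposure falls.

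**Step 2: starting dose.** Take an ESA type with half its patients on D weekly and half on 3D every 3 weeks (assumed mix).

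- Mean recorded dose = 0.5 x D + 0.5 x 3D = 2D, a dose that no patient received.
- Dose per week = D / 1 = 3D / 3 = D for every patient.

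The quartiles and range that Section 9.7.2.1 also asks for would run from D to 3D. That shows spread but not that the spread is schedule alone.

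**Step 3: rapid rise with no later reduction.** Let r be the share of rapid risers whose ESA was truly reduced, and q the share of those reductions made by the interval alone. If interval-only reductions are not counted and nothing else goes wrong:

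reported share without reduction = 1 - r x (1 - q), against a true 1 - r.

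| r (assumed) | True share | q = 10% | q = 30% | q = 50% |
|---|---|---|---|---|
| 70% | 30% | 37% | 51% | 65% |
| 50% | 50% | 55% | 65% | 75% |

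For example, 1 - 0.7 x (1 - 0.3) = 1 - 0.49 = 51%. Both r and q are assumptions, because the protocol gives neither. Changes such as rows 3 and 4 of the first table, coded as decreases, would pull the reported share the other way.

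**The case against.** The strongest reply is that the protocol contains no comparison algorithm. It says that raw values are recorded and categorised, but not that two successive doses are compared without regard to interval, and such a derivation may properly be left to the SAP. Section 9.7.2.4 reports the type of modification where available and with an open list of examples, and the abstract takes reductions from the medical notes. A lengthened interval that the chart calls a reduction could then count. The inputs for a better derivation are also planned: prescription dates, administration times if available, frequency where available, dose, and the duration of each prescription. Section 9.3.4 already lets sites mark an item as unknown, so making the frequency field mandatory would add little.

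Much of this stands, and it rules out saying that misclassification is certain. It does not remove the point. Section 9.3.1 places modification under dose, names raw values and gives a closed list, and Section 9.7.2.4 summarises starting dose by ESA type with no reference to schedule. Relying on the notes helps only where abstractors treat a longer interval as a reduction. No rule says so, and Section 9.3.4 itself accepts that abstractors may interpret charts differently.

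A reader might also infer that a switch between ESAs will be recorded as a dose change across incompatible units. No section compares doses across agents, so this does not follow; a switch simply has no assigned category. Nor do the different groupings in Sections 8.2 and 9.7.2.5.1 show a conflict in the data. Nothing identifies a patient whom they would place differently, so this is a matter of aligning wording.

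**Conclusion.** The point holds as a weakness in two definitions for secondary, descriptive outcomes. As written, starting doses on different schedules are pooled within ESA type. Schedule changes may be coded as increases or decreases when weekly exposure is unchanged, and reductions made only through the interval may be missed unless the notes call them reductions. Missed reductions would inflate the share of rapid risers with no response. The primary outcome, Hb at index, is not affected.

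The size is unknown. The distortions in the first table are exact for the schedules shown, but how often such changes occur within the 9-week follow-up is not stated, and the 37% to 75% range in step 3 rests wholly on assumed inputs. A reader might conclude that schedule changes will be counted as escalations, that a known share of reductions will be lost, or that the error runs only one way. The protocol supports none of these.

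**What to change.** In Sections 9.3.1 and 9.7.2.4:

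- Where the interval is recorded, or can be derived from prescription or administration dates, derive dose per week for each prescription as dose divided by interval, within the same ESA product. Prescription dates give the interval only if each prescription covers one administration, so the derivation should state when they may be used.
- Classify increase and decrease on dose per week. Show changes made by the interval alone, and switches of ESA, as their own categories.
- Use the same definition in the rapid-rise endpoint, so that a fall in dose per week is recognised whichever way it was made.
- Report starting dose per week, with the raw dose by interval beside it.
- Use one wording for the ESA grouping in Sections 8.2, 9.7.2.4 and 9.7.2.5.1.

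The cost is one derived variable and revised wording in those sections; the inputs are already among the planned items. The downside is that prescriptions with unknown interval cannot be classified. They should be counted and reported as not classifiable rather than as unchanged. This is a measurement definition only; it proposes no dose, schedule or rule for adjusting treatment.
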